2.2. Pooling Algorithm for Analysis Centers

All centers will be pooled. In another words, center will not be included in any statistical model.

2.3. Definition of Trial Dates

The following trial date definitions apply to Part 1 of the study.

Trial reference start date is defined as the date of randomization of the subject.

Trial reference end date is defined as the date of the last trial-related procedure for the subject; specifically, it is equal to the maximum of the following dates:

- Dates of all study-related visits (including scheduled or unscheduled visits)
- Dates of all study-related procedures, findings and events, including, but not limited to, safety and efficacy endpoint events, adverse events, concomitant medications, disposition, and death

First dose date is defined as the date on which the first dose of study drug is taken by the subject. If this date is missing or incomplete for a subject who takes study drug, the first dose date is set to the earliest logically possible date on or after randomization. More specifically, the first dose date is defined as the maximum of the randomization date and the first day of the month if only day is missing; it is defined as maximum of the randomization date and the first day of the year if day and month are missing.

Last dose date is defined as the date on which the last oral (apixaban) dose of study drug is taken by the subject. If this date is missing or incomplete for a subject who takes study drug, the last dose date is in general set to the date of the last visit at which oral (apixaban) study drug is dispensed plus the number of pills in the drug bottle(s) dispensed at that visit, but can't be later than the trial reference end date. In cases where study is still ongoing, data cut-off date will be used as the last dose date

Last outcome-evaluation date is defined as the date of the last study visit (in clinic or phone contact) while the subject is alive at which the outcome status of bleeding and efficacy endpoints is evaluated, or the date of death.

2.4. Analysis Sets

Two elements define an analysis set:

- The analysis population, which specifies those subjects who will be included in an analysis
- The observation (or analysis) period, which specifies the time window within which data will be included in an analysis

2.4.1. All Enrolled Analysis Set

The all enrolled analysis set is not used in this study

2.4.2. All Randomized Analysis Set

The all randomized analysis set includes all subjects who were randomized in the study.

2.4.3. Efficacy Analysis Set(s)

Remarks: - The endpoints of the study will be the same for Parts 1 and 2 although the focus of Part 1 will be primarily dose escalation based on safety while the focus of Part 2 will primarily be the assessment of dose response in both safety and efficacy.

2.4.3.1. Primary Efficacy Analysis Set

Modified Intent to Treat (mITT) analysis set includes all randomized subjects with an evaluable venography assessment or a confirmed symptomatic VTE event, or any death.

2.4.3.2. Secondary Efficacy Analysis Set

Efficacy Per Protocol analysis set includes all randomized subjects with no major protocol deviations and an evaluable venography assessment within 24 hours after the last dose of the oral study drug or with confirmed symptomatic VTE within 2 days of the last dose of oral study drug, or any death within 2 days of the last dose of oral study drug. Subjects without symptomatic VTE or death must also have received the single complete infusion of JNJ-64179375 or at least 18 doses of oral apixaban

Efficacy Per Protocol analysis set details: Efficacy Per Protocol analysis set includes all randomized subjects in the Up to Day 10-14 visit observation period with: -

- No major protocol deviations (see section 4.5 for major protocol deviation)
→ this is expected to come from Data Management
- Subject evaluable venography assessed within 24 hours after the last dose of oral study drug
→ That is, last dose date < venography assessment date ≤ last oral (Apixaban) dose date + 1 day
- Subject confirmed centrally adjudicated symptomatic VTE within 2 days of the last dose of oral study drug.
→ that is, confirmed symptomatic VTE date ≤ last oral (apixaban) dose date + 2 days
- Subject any death within 2 days of the last dose of oral study drug
→ that is, any death date ≤ last oral (apixaban) dose date + 2 days
- Subject without symptomatic VTE or death received the single complete infusion of JNJ-64179375 or at least 18 doses of oral apixaban.
→ that is, in the “Study Drug Administration” eCRF form for JNJ-64179375, “Was the Total administered?” should be equal to “Yes” or for apixaban, total # doses ≥18.

The 2 observation periods to be used in the efficacy analyses sets include the following:

- Up to Day 10-14 visit (venography assessment)
- Up to the Week 18 visit

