2.4.4. Safety Analysis Set

Safety analysis set includes all randomized subjects who received at least 1 dose (partial or complete) of active study drug

Safety Per Protocol analysis set includes all randomized subjects with no major protocol deviations who received the single complete infusion of JNJ-64179375 or at least 18 doses of oral apixaban or with a bleeding event centrally adjudicated by the Clinical Events Committee (CEC) within 2 days of the last dose of oral study drug

Safety Per Protocol analysis set details: Safety Per Protocol analysis set includes all randomized subjects, in the Up to Day 10-14 visit observation period with:

- No major protocol deviations (see section 4.5 for major protocol deviation)
→ this is expected to come from Data Management
- Subject received the single complete infusion of JNJ-64179375 or at least 18 doses of oral apixaban
→ that is, in the “Study Drug Administration” eCRF form for JNJ-64179375, “Was the Total administered?” should be equal to “Yes” or for apixaban, total # doses ≥ 18 .
- Subject bleeding event centrally adjudicated by the CEC within 2 days of the last dose of oral study drug
→ that is, CEC adjudicated bleeding event date \leq last oral (apixaban) dose date + 2 days

The 3 observation periods to be used in the bleeding event analyses include the following:

- Up to Day 10-14 visit (venography assessment)
- Up to the Week 5 visit
- Up to the Week 18 visit

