4.1. Demographics and Baseline Characteristics

Table 4 presents a list of the demographic variables that will be summarized by treatment group, combined JNJ-64179375 treatment group, and overall for the safety analysis set(s).

Table 4: Demographic Variables

Continuous Variables:	Summary Type
Age (years)	Descriptive statistics (N, mean, standard deviation [SD], median and range [minimum and maximum]
Weight (kg)	
Height (cm)	
Body Mass Index (BMI) (kg/m ²)	
Categorical Variables	Frequency distribution with the number and percentage of subjects in each category.
Age (18-<50, 50 - <65, 65 - <75, ≥ 75)	
Sex (male, female, undifferentiated)	
Race ^a (American Indian or Alaska Native, Asian, Black or African American, Native Hawaiian or other Pacific Islander, White, Other, Multiple)	
Ethnicity (Hispanic or Latino, not Hispanic or Latino)	
BMI ([underweight <18.5 kg/m ² , normal 18.5-<25 kg/m ² , overweight 25-<30 kg/m ² , obese ≥30 kg/m ²])	

^aIf multiple race categories are indicated, the Race is recorded as 'Multiple'
The following analyses sets (Table 5) will be summarized by treatment group.

Table 5: Analysis Sets

Categorical Variables	
Efficacy (mITT, Per-protocol)	Frequency distribution with the number and percentage of subjects in each category.
Safety* (Safety, Per-protocol)	
All Randomized	All randomized will only be used to summarize subject disposition

*Bleeding event analysis will be based on both safety and per-protocol analysis sets; Adverse events will be based on safety analysis set only

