4.4. Extent of Exposure

The number and percentage of subjects who receive study agent will be summarized by treatment group

Descriptive statistics for study agent duration (N, mean, SD, median, and range (minimum, maximum) will be presented by treatment group for the safety analysis set.

Duration of exposure for apixaban will be summarized in the following duration categories <1, 2 - <5, 5- <10, 10- <15, ≥ 15 days by treatment group.

Study agent duration is defined as (date of last oral (apixaban) dose of study agent – date of first dose of study agent) +1.

Total dose days of exposure is defined as the total number of days that study agent was administered to the subject (excluding days of study agent interruption).

The total number of dose administrations received will be summarized in the following count categories 1, 2 - <5, 6- <9, 10- <15, 16- <20, 20- <29, ≥ 29 by treatment group.

Descriptive statistics will be presented for the following parameters:

- Number of administrations

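### Two SAP date rules do not do what they say: the 24-hour per-protocol venogram rule accepts only next-day venograms, and a missing last oral dose is imputed at one capsule a day instead of two.

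*SAP*

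**What the plan says.** **Venogram window.** SAP 2.4.3.2 and Protocol 11.1 both state the Efficacy Per Protocol criterion as an evaluable venogram no later than 24 hours after the final oral dose. The SAP then gives the programming rule: "last dose date < venography assessment date ≤ last oral (Apixaban) dose date + 1 day". SAP 2.3 defines the last dose date as "the date on which the last oral (apixaban) dose of study drug is taken by the subject", with no clock time.

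**Missing last oral dose.** SAP 2.3 sets a missing or incomplete date, in general, to the date of the last dispensing visit "plus the number of pills in the drug bottle(s) dispensed at that visit", "but can't be later than the trial reference end date". The next sentence covers an ongoing study: "data cut-off date will be used as the last dose date".

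**Where the date is used.**
- Exposure (SAP 4.4): "Study agent duration is defined as (date of last oral (apixaban) dose of study agent" minus the first dose date, plus 1, with categories that include 10 to under 15 days and 15 days or more.
- The venogram rule and the event clauses of the Efficacy Per Protocol set (SAP 2.4.3.2), which accept symptomatic VTE or death up to the last oral dose date plus 2 days.
- The Safety Per Protocol set (SAP 2.4.4), through the clause "Subject bleeding event centrally adjudicated by the CEC within 2 days of the last dose of oral study drug". The footnote to SAP Table 5 says "Bleeding event analysis will be based on both safety and per-protocol analysis sets".

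**The concern.** A 24-hour window counts elapsed hours, while the programmed rule compares calendar days. The two can disagree in both directions, dropping compliant same-day venograms and keeping late next-day ones. Same-day venograms are foreseeable: the Time and Events Schedule puts study drug administration and venography at the same Day 10-14 visit, and the protocol only requires the venogram to follow the last capsule.

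Adding a capsule count to a date treats each capsule as one day, but the regimen is two a day. Nothing in SAP 2.3 divides by two or limits the result to the dosing phase. The cut-off sentence is not limited to subjects still dosing, and the SAP does not say which of the two rules governs the Part 1 Topline report.

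At stake are correct per-protocol membership, correct exposure summaries, and a possible tilt in the per-protocol bleeding comparison. Under-dosed subjects enter the Safety Per Protocol set only if they bled, so a last dose date that is too late can add bleeders but never non-bleeders.

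**Working it through.** **1. Venogram rule.** Let d be the last dose date and v the venogram date, both whole days. The condition d < v ≤ d + 1 has one solution, v = d + 1. The elapsed time it admits runs from just over 0 to just under 48 hours, provided midnight is crossed. It admits no same-day gap.

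Assume capsules at 08:00 and 20:00 and venography between 09:00 and 17:00 (the documents give no clock times):

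| Last capsule | Venogram | Gap | 24-hour criterion | SAP rule |
|---|---|---|---|---|
| 08:00 | same day | 1–9 h | met | excluded |
| 08:00 | next day | 25–33 h | not met | included |
| 20:00 | next day | 13–21 h | met | included |

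The rule is therefore wrong both ways after a morning last capsule and right after an evening one.

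**2. Pill-count imputation.** Inputs: 30 capsules per bottle (Protocol 14.2); twice daily for 10 to 14 days (Protocol 6); bottle dispensed at randomization, taken here as Day 1 with no later dispensing (SAP 1.5).
- As written: Day 1 + 30 = Day 31; duration = 31 − 1 + 1 = 31 days.
- Actual supply: 30/2 = 15 days.
- Excess over planned dosing: 31 − 14 = 17 to 31 − 10 = 21 days. Ratio: 31/14 = 2.2 to 31/10 = 3.1.
- The subject moves from the 10 to under 15 day category to the 15 days or more category.
- The cap does not bind once a Week 5 visit has taken place at its target, Day 35.
- With Day 31 imputed, every Day 10-14 venogram fails the rule in step 1, because it precedes the supposed last dose.

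Effect on mean apixaban duration, assuming a true mean of 12 days and k missing dates among n subjects: k × (31 − 12)/n.

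| n (apixaban, about 10 per cohort) | k = 1 | k = 2 |
|---|---|---|
| 10 (one cohort) | 1.9 days | 3.8 days |
| 30 (three cohorts) | 0.63 | 1.27 |
| 60 (six cohorts) | 0.32 | 0.63 |

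**3. Cut-off rule.** The documents give no cut-off day. If it fell on a subject's Day 30, 60 or 126, the imputed duration would be 30/14 to 30/10 = 2.1 to 3.0 times the planned duration, 60/14 to 60/10 = 4.3 to 6.0 times, or 126/14 to 126/10 = 9.0 to 12.6 times. This is an alternative to step 2, not an addition to it.

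**4. Safety Per Protocol set.** Suppose an apixaban subject takes 9 capsules, the last on Day 5, and the date is missing.
- Correct clause: Day 5 + 2 = Day 7.
- As written: Day 31 + 2 = Day 33, so any bleed up to the Day 10-14 visit counts. That is 3 extra days (Days 8–10) to 7 extra days (Days 8–14).
- Illustrative effect of one such bleeder on the apixaban rate: 2/29 (6.9%) becomes 3/30 (10.0%), up 3.1 points; or 4/59 (6.8%) becomes 5/60 (8.3%), up about 1.6 points.

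A JNJ-64179375 subject with a complete infusion qualifies regardless of the oral dose date, so the effect falls mainly on apixaban.

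**The case against.** **The strict inequality may be a deliberate, conservative convention.** Venography must follow the last capsule, and dates alone cannot order two events on the same day. This explains the exclusion of same-day venograms if times are not recorded, and the documents do not say whether they are. It does not explain accepting next-day venograms beyond 24 hours, and the SAP does not present the rule as an approximation or say that date means date-time.

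**The imputation is hedged and capped.** The text says in general, but supplies no other rule. The cap does bind for a subject with no contact after the Day 10-14 visit, and the exposure figure is then close to the truth. The imputed last dose then falls on the visit day, however, so a venogram on that day still fails the strict inequality.

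**Missing dates should be uncommon.** Bottles are returned and counted at the Day 10-14 visit (Protocol 7), and sites need the last dose time to schedule the venogram. This stands.

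**The bleeding tilt needs several rare conditions together:** an apixaban subject, fewer than 18 doses, a missing date, and an adjudicated bleed more than 2 days after the true last dose but before the visit. Such a subject might also be removed first as a major deviation under SAP 4.5. This stands as a limit on frequency. It does not change the direction of the error.

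**The reach is small.** SAP 5.2.3 puts VTE incidence on mITT, and no Part 1 VTE outcome analysis is assigned to the Efficacy Per Protocol set. SAP 6.1.2 puts bleeding incidence on the safety set. This also stands.

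**Conclusion.** Both rules are wrong as written. The venogram rule does not implement the 24-hour criterion stated beside it, and the imputation puts a full bottle's last dose at Day 31 when the supply lasts 15 days. The Day 31 result assumes a missing date, one full bottle dispensed on Day 1, and follow-up past Day 31. The clock times, the 12-day true mean, the cut-off days and the bleeding counts are illustrations, not estimates.

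The consequences are wrong per-protocol membership, overstated exposure for subjects with a missing date, and a possible rise in the apixaban bleeding rate in the Safety Per Protocol set, which would favour JNJ-64179375. VTE results on mITT, bleeding results on the safety set, the escalation thresholds and the sample size do not change. The number of subjects affected cannot be derived from the documents. The rules should be corrected before database lock, but they do not threaten the main Part 1 conclusions.

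**What to change.** **Venogram window.** Define it on date-times: more than 0 and at most 24 hours after the last oral dose. If a time is missing, accept the day after the last dose date, and accept the same date only where the record shows that the venogram followed the last capsule. Flag these subjects and state that the fallback can admit some venograms beyond 24 hours.

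**Imputation.** Set the last oral dose to the first dose date + (capsules dispensed − returned)/2, rounded up, − 1 day, capped at the Day 10-14 visit. If the bottle is not returned, use capsules dispensed/2 with the same cap. For example, 24 capsules taken gives Day 12, so a Day 13 venogram qualifies through the date fallback; under the current rule (Day 31) it fails. For the 9-capsule subject above the formula gives Day 5.

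**Cut-off.** Apply the data cut-off date only to subjects still in the dosing phase at cut-off. List every subject with an imputed date.

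**Cost.** SAP wording and programming only; dispensing and returns are already tracked in the IWRS. Some error remains. Without capsule times, some 25–33 hour venograms are still kept. The count-based date is about one day early for every two missed capsules, or if only one capsule was taken on Day 1. With an unreturned bottle the date falls on the visit day: the 2-day event clause still reaches that visit, but the venogram counts only if the record shows that it came after the last capsule.

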2.4.4. Safety Analysis Set

Safety analysis set includes all randomized subjects who received at least 1 dose (partial or complete) of active study drug

Safety Per Protocol analysis set includes all randomized subjects with no major protocol deviations who received the single complete infusion of JNJ-64179375 or at least 18 doses of oral apixaban or with a bleeding event centrally adjudicated by the Clinical Events Committee (CEC) within 2 days of the last dose of oral study drug

Safety Per Protocol analysis set details: Safety Per Protocol analysis set includes all randomized subjects, in the Up to Day 10-14 visit observation period with:

- No major protocol deviations (see section 4.5 for major protocol deviation)
→ this is expected to come from Data Management
- Subject received the single complete infusion of JNJ-64179375 or at least 18 doses of oral apixaban
→ that is, in the “Study Drug Administration” eCRF form for JNJ-64179375, “Was the Total administered?” should be equal to “Yes” or for apixaban, total # doses ≥ 18 .
- Subject bleeding event centrally adjudicated by the CEC within 2 days of the last dose of oral study drug
→ that is, CEC adjudicated bleeding event date \leq last oral (apixaban) dose date + 2 days

The 3 observation periods to be used in the bleeding event analyses include the following:

- Up to Day 10-14 visit (venography assessment)
- Up to the Week 5 visit
- Up to the Week 18 visit

2.4.5. Pharmacokinetics Analysis Set

The PK analysis set is defined as subjects who have received least one dose of JNJ-64179375 and have at least one valid blood sample drawn for population PK model development.

2.4.6. Immunogenicity Analysis Set

The immunogenicity analysis set is defined as all subjects who received at least one dose of JNJ-64179375 and have appropriate plasma samples for anti-JNJ-64179375 antibody detection.

2.4.7. Pharmacodynamics Analysis Set

The PD analysis set is defined as subjects who have received at least one dose of JNJ-64179375 and have at least one valid blood sample drawn for measurement.

2.5. Definition of Subgroups

No subgroup analysis is planned in Part 1.

2.6. Study Day and Relative Day

Study Day 1 or Day 1 refers to the start of the first study agent administration or randomization date. All efficacy and safety assessments at all visits will be assigned a day relative to this date.

Study day or relative day for a visit is defined as:

- Visit date - (date of Study Day 1) +1, if visit date is \geq date of Day 1
- Visit date - Date of Day 1, if visit date < date of Day 1

There is no 'Day 0'

2.7. Baseline and Endpoint

Baseline is defined as the last observation prior to the start of the first study agent administration or randomization date.

Endpoint is defined as the last available postbaseline result within the analysis period. Unscheduled visit results are included in this definition and will be considered as the endpoint value if the unscheduled visit result is the last postbaseline result available within the analysis period. The result refers to an event.

2.8. Imputation Rules for Missing AE Date/Time of Onset/Resolution

Partial AE onset dates will be imputed as follows:

- If the onset date of an adverse event is missing day only, it will be set to:
 - First day of the month that the AE occurred, if month/year of the onset of AE is different than the month/year of the earliest study agent start.
 - The day of study agent start, if the month/year of the onset of AE is the same as month/year of the earliest study agent start date and month/year of the AE resolution date is different.
 - The day of study agent start or day of AE resolution date, whichever is earliest, if month/year of the onset of AE and month/year of the earliest study agent start date and month/year of the AE resolution date are same.
- If the onset date of an adverse event is missing both day and month, it will be set to the earliest of:
 - January 1 of the year of onset, as long as this date is on or after the earliest study agent start date,
 - Month and day of the earliest study agent start date, if this date is in the same year that the AE occurred,
 - Last day of the year if the year of the AE onset is prior to the year of the earliest study agent start date,
 - The AE resolution date.
- Completely missing onset dates will not be imputed.

Partial AE resolution dates not marked as ongoing will be imputed as follows:

- If the resolution date of an adverse event is missing day only, it will be set to the earliest of the last day of the month of occurrence of resolution or the day of the date of death, if the death occurred in that month.
- If the resolution date of an adverse event is missing both day and month, it will be set to the earliest of December 31 of the year or the day and month of the date of death, if the death occurred in that year.
- Completely missing resolution dates will not be imputed.

AE onset/resolution dates with missing times will be imputed as follows:

- A missing time of onset of an adverse event will be set to the earlier of:
 - 00:01 as long as the onset date is after the study agent start date,
 - The time of the study agent start if this is the same day the AE occurred.
- The missing time of resolution of an adverse event will be set to 23:59.

If a missing time is associated with a partial or missing date, the date will be imputed first prior to imputing the time.

Remarks: Imputation rules for missing Event dates will follow similar rules as for AEs.

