5.2.1. Definition

Total VTE is defined as the composite of proximal and/or distal DVT (asymptomatic confirmed by venography assessment of the operated leg or objectively confirmed symptomatic), nonfatal PE, or any death.

→ Total VTE = Proximal DVT (Asymptomatic or Symptomatic) + Distal DVT (Asymptomatic or Symptomatic) + Nonfatal PE + Any death

The primary window for analysis of Total VTE is the up to Day 10-14 visit observation period.

The following maps the locations in eCRF of the investigator reported components needed in the definition of total VTE:

Total VTE Component	eCRF Form name (s)	Comments
Symptomatic DVT (Proximal or Distal)	Suspected Symptomatic Deep Vein Thrombosis	In the opinion of the investigator, does this event meet the protocol definition of Symptomatic Deep Vein Thrombosis? YES
Asymptomatic DVT (Proximal or Distal)	Planned Day 10-14 Venography	Proximal clot or Distal clot
Nonfatal PE	Suspected Symptomatic Pulmonary Embolism & Death	Suspected symptomatic PE & Alive
Death	Death	

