6.1.1. Definition

Any bleeding event is defined as the composite of major, CRNM, and minimal bleeding events

- Any bleeding = Major + CRNM + Minimal

The primary window for analysis of any bleeding event is the up to Day 10-14 visit observation period.

The following maps the location in eCRF of the investigator reported components needed in the definition of any bleeding:

Any bleeding	eCRF Page # (s)	Comments
Bleeding Category	Bleeding Event	Classify the bleeding category as defined in Attachment 2 of the protocol: 
 • Major Bleeding in Surgical Setting • Clinically Relevant Nonmajor Bleeding • Minimal Bleeding

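### SAP 2.8 extends an earliest-date rule to endpoint events, so a bleed with the day missing that began after the Day 10-14 visit can be counted in the primary window, against the visit record

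*SAP*

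**What the plan says.** SAP 2.8 gives three rules for an adverse event whose onset lacks only the day:

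- Onset month differs from the dosing month: "First day of the month that the AE occurred, if month/year of the onset of AE is different than the month/year" of dosing.
- Onset in the dosing month, resolution in another month: "The day of study agent start, if the month/year of the onset of AE is the same as month/year" of dosing.
- Onset, dosing and resolution all in one month: "The day of study agent start or day of AE resolution date, whichever is earliest".

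A wholly missing onset is left alone: "Completely missing onset dates will not be imputed". A closing remark carries the scheme over to endpoints: "Imputation rules for missing Event dates will follow similar rules as for AEs".

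The endpoints are cut by time. For bleeding, SAP 6.1.1 says: "The primary window for analysis of any bleeding event is the up to Day 10-14 visit observation period". For VTE, SAP 5.2.1 says: "The primary window for analysis of Total VTE is the up to Day 10-14 visit observation period". SAP 2.4.4 adds separate bleeding periods to Week 5 and Week 18.

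Neither document gives a separate date rule for endpoint events, a check against the last event-free visit, a sensitivity analysis for imputed dates, or an expected number of partial dates.

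**The concern.** Taking the earliest possible date is sensible when the question is whether an event is treatment-emergent, because a doubtful event is then kept. The endpoint analysis asks a different question: did the event start before or after the Day 10-14 visit? For that question the rule can err in one direction only.

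The rule also ignores better evidence. Protocol 9.7.2.1.1 has bleeding checked at every visit. Protocol section 12 has subjects asked directly about bleeding, including bruising, gingival bleeding and epistaxis. A bleed absent at the Day 10-14 visit and first reported at Week 5 lies between two known dates, yet SAP 2.8 can date it to Day 1.

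Two uses are exposed. Any bleeding is a focus of the end-of-Part-1 review that selects doses for Part 2, by which time earlier cohorts may have Week 5 data. It also feeds a suggested escalation criterion in SAP 3.1.1. Part 1 groups are small (about 40 JNJ-64179375 and 10 apixaban subjects per cohort), so single events carry weight.

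**Working it through.** The plan states no figure for the effect of date imputation, so there is none to reproduce. The check applies the rule to every possible dosing date.

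**Inputs from the documents.** The three missing-day rules (SAP 2.8). Study day = date − Day 1 date + 1 (SAP 2.6). Primary window up to the Day 10-14 visit, so the cut is taken at Day 10, 12 and 14. Next visit at Week 5 ± 1 week (Time and Events Schedule), at latest 6 × 7 = Day 42. Follow-up to Week 18, 18 × 7 = Day 126.

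**Assumptions not in the documents.** Only the day is missing; dosing dates are uniform over a calendar year; onset is uniform over the stated band; the endpoint rule equals the AE rule.

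**Three examples.**
- Dosed 5 March, true onset 25 March (Day 21): same month, set to 5 March = Day 1. Pulled in.
- Dosed 20 March, true onset 20 April (Day 32): set to 1 April = Day 13. Pulled in at a Day 14 cut.
- Dosed 5 March, true onset 10 April (Day 37): set to 1 April = Day 28. Not pulled in.

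**How often the next 1st is early enough.** The 1st of the next month is Day 14 or earlier when dosing falls in the last 13 days of a month: 12 × 13 = 156 dates, and 156/365 = 42.7%.

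**Full enumeration.** 365 dosing dates × 28 onset days (Day 15-42) = 10,220 combinations; × 112 onset days (Day 15-126) = 40,880.

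| True onset | Cut Day 10 | Cut Day 12 | Cut Day 14 |
|---|---|---|---|
| Day 15-42 | 4,033/10,220 = 39.5% | 4,679/10,220 = 45.8% | 5,348/10,220 = 52.3% |
| Day 15-126 | 4,033/40,880 = 9.9% | 4,679/40,880 = 11.4% | 5,373/40,880 = 13.1% |

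Of the 52.3%, 16.8 points are same-month events set to Day 1. The other 35.5 points come from the 1st of the next month. At the Day 14 cut the share by week of true onset is 87% (Day 15-21), 64% (Day 22-28), 41% (Day 29-35) and 18% (Day 36-42). It is zero from Day 45. If onset is front-loaded within Day 15-42, with a half-life of 7 to 28 days, the share is 71% to 58%.

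**Direction.** For a true post-dose onset the imputed date is never later than the true date and never before Day 1. No event inside the window can move out; the enumeration gives 0 at each cut.

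**Sensitivity of the decision.** With the SAP's Miettinen-Nurminen method, the one-sided 90% lower bounds for the three SAP Table 3 examples, as printed and with one JNJ-64179375 event fewer, are:

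| JNJ-64179375 vs apixaban | Lower bound | One fewer | Lower bound |
|---|---|---|---|
| 8/25 vs 1/10 | +0.9% | 7/25 | −2.9% |
| 5/25 vs 1/20 | +2.1% | 4/25 | −1.5% |
| 9/50 vs 3/40 | +1.3% | 8/50 | −0.5% |

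The first column of bounds matches the SAP's rounded 1%, 2% and 1%.

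**The case against.** The strongest reply is about size. The shares apply only once the day is missing, and the plan makes that uncommon. Subjects should return for unscheduled assessment of any potential bleed (protocol 9.1.3). PK samples with an exact date and time are due soon after one (9.3.1). Endpoint events have their own eCRF forms, entries are queried, and the CEC adjudicates from source documents. This stands: the effect on any event rate cannot be computed and is probably small.

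The Table 3 flips are also partly generic. Those cells sit at the boundary, and the criteria are suggestions weighed with all other data. A misdated bleed matters only for a subject with no true bleed in the window. This stands too: the flips show that one event can matter, not that one will.

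Over-counting bleeds is arguably the cautious choice in a dose-escalation safety part. That is fair, but it supports an earliest-date sensitivity analysis better than a primary analysis that overrides the visit record.

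Finally, the SAP says the rules will be similar, not identical. The enumeration is therefore conditional on applying them as written, and the exact endpoint rule is left open.

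Two stronger readings are tempting. A reader might infer that the error falls mainly on JNJ-64179375, since its half-life is about 25 days while apixaban stops at 10 to 14 days. The documents give no late bleeding rates by arm and the rule applies to all arms, so this is a mechanism without a size. A reader might also infer that the rule pulls off-drug apixaban VTE into the window and so favours JNJ-64179375. Planned venography, imaging-confirmed DVT or PE, and death will rarely lack a day, so this is close to hypothetical.

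**Conclusion.** The point holds as a defect in a stated rule, with an unknown and probably small effect. If the AE rule is applied to endpoint events as written, late bleeds with a missing day can only move into the primary window. Of those with true onset on Day 15-42, 40% to 52% do so (cut Day 10 to Day 14). Of those on Day 15-126, 13% do so at the Day 14 cut.

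These shares rest on uniform dosing and onset dates and on a missing day. The Day 15-42 band ends at the latest nominal Week 5 visit; a wider band lowers the share and front-loaded onset raises it. They are not shares of all bleeding events. The exposure is mainly investigator-reported minor bleeds, which count in the primary safety endpoint. No between-arm bias and no VTE effect can be sized. A correction is still worthwhile because the visit data that would prevent the error are already collected.

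**What to change.** In SAP 2.8, keep the present rule for treatment emergence and replace the closing remark with a rule for endpoint events:

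1. For a bleeding event with a partial date (and any VTE event with one), impute the earliest date that lies in the recorded month, after the last visit at which the subject was assessed and the event was not reported, and not after the visit at which it was reported.
2. If no date meets both constraints, the recorded month takes precedence.
3. Report the number of endpoint events with imputed dates, by treatment group.
4. Repeat the any-bleeding analysis under the present earliest-date rule as a conservative sensitivity analysis.

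For a subject assessed at the Day 10-14 visit whose bleed truly began afterwards, a date meeting both constraints always exists, because the true date is one. Such an event can then no longer be placed in the primary window.

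The downside is that a bleed which began on, say, Day 8, was forgotten at the Day 10-14 visit and was reported at Week 5 without a day could move out of the window. Step 4 would show this. The cost is a few sentences, a short derivation from visit dates already held, and one additional table.
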